3.0 STUDY FLOW AND FOLLOW-UP SCHEDULE

3.1 Number of Subjects

Eligible consecutive patients that present for a MitraClip procedure should be consented. Once a patient has provided written informed consent, the patient is considered enrolled. Upon echocardiographic verification that there is no evidence of intracardiac, inferior vena cava (IVC) or femoral venous thrombus per IFU requirements; the MitraClip procedure should be attempted for all enrolled patients. A procedure is considered attempted when the MitraClip delivery system is introduced into the femoral vein. Only enrolled patients with an attempted MitraClip procedure will be included in the analysis population. Patients that have an attempted procedure, but no MitraClip implant will be followed for 30 days only.

Patients that do not give consent or patients with a thrombus identified on the pre-treatment echocardiogram are not eligible for the EXPAND Study and will not be part of the analysis population. If the thrombus is medically treated and resolved at a later date, a patient may be re-consented for the EXPAND Study if they are eligible for a new attempted MitraClip procedure.

Up to 1,000 consented subjects with confirmation of no thrombus who have a MitraClip procedure attempted will be included for analysis in *the MitraClip EXPAND Study*. The Study will be conducted at a maximum of 60 centers in the EU and the US. A site maximum of 100 subjects will be enforced so that no site will be permitted to submit data for more than 10% of the study population.

3.2 Overall Flow of the Study and Follow-up Schedule

[figure not shown]
Enrolled patients that receive a MitraClip implant should undergo study follow-up per standard of care. Follow-up data on clinical assessment should be submitted for a 30-day visit, 6-month visit or phone call and 12-month visit. Echocardiograms are required to be submitted for the baseline, discharge, 30-day and 12-month time points. All Echocardiograms conducted during the study period (required by protocol or not) will be collected by the Sponsor (see **Table 2** for the Clinical Assessment Schedule). Patients that have an attempted procedure, but no MitraClip implant will be followed for 30 days only.

The first 220 European patients treated with the MitraClip XTR in *the MitraClip EXPAND Study* with evaluable APS data will be included in the XTR PMCF Study as described in Appendix 1.

Subjects with evaluable echocardiograms may be selected for a more detailed assessment by an independent core lab. Pre-defined criteria will be used to identify eligible subjects for this assessment. A minimum of 100 subjects will be randomly selected from this eligible population.

Figure 3 outlines the flow of the Study.

Figure 3: Study Flow

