5.10 Study Completion

A Study Completion eCRF must be completed when:

- the subject is considered lost to follow-up per the above definition or
- the subject withdraws from the Study or
- the investigator withdraws the subject from the Study or
- the subject has died or

- upon Study completion (e.g., 1 year follow-up time point has been reached) or
- sponsor termination of Study

Sponsor must be notified of the reason for subject discontinuation. The site will provide this information on the electronic case report form (eCRF). Investigators must also report this to their EC/IRB as defined by their institution's procedure. Subjects will not be replaced.

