4.3 Success Criteria

The MitraClip XTR PMCF Study will be successful if the lower one-sided 95% confidence interval (CI) of the observed APS rate for the study is greater than the Performance Goal (PG) of 80.7%.

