6.3 Post-procedure

Post treatment TTEs/TEES, Clinical Assessments and Laboratory / Clinical Tests should be conducted per standard of care. Post-procedure information to be reported for this study include at minimum: adverse events, MR severity and New York Heart Association (NYHA) Functional Class.

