9.2 Analysis Populations

9.3 Sample Size Calculations and Assumptions

The sample size of a minimum 220 subjects is determined based on the endpoint of APS. APS is defined as successful implantation of the MitraClip Implant with resulting MR severity of 2+ or less on discharge Echocardiogram.

The powered endpoint of APS will be evaluated against a pre-specified clinical performance goal (PG). The power calculation is based on the following statistical hypotheses and assumptions:

- H₀: APS rate ≤ PG
- H_A: APS rate > PG

- [REDACTED]
- One-sided type I error rate = 0.05

[REDACTED]

[REDACTED]

The sample size calculation was performed using PASS 15 (Hintze J, 2017, NCSS, LLC. Kaysville, Utah).

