9.4.1 Primary Endpoint Analysis

The exact test against PG will be performed for the primary endpoint in the analysis population. The null and alternative hypotheses will be of the following form:

H_0 : APS rate \leq PG

H_A : APS rate $>$ PG

APS is the Acute Procedural Success.

[REDACTED]

[REDACTED]

[REDACTED]

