9.4.4 Procedures for Accounting for Missing, Unused or Spurious Data

If Echocardiography assessed MR severity at discharge is unavailable or cannot be assessed, the 30-day value will be used to assess APS. All analyses will be based on available data with missing data excluded. Any unused or spurious data will be noted as appropriate

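### Patients whose acute procedural success cannot be evaluated drop out of the only powered test, the two definitions of the XTR set disagree, and no sensitivity analysis is visible

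*Protocol*

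**What the plan says.** The XTR post-market study (Protocol Appendix I) has one powered endpoint, acute procedural success (APS). On sample size, Appendix I 9.3 says: "The sample size of a minimum 220 subjects is determined based on the endpoint of APS". The study succeeds if the lower one-sided 95% bound "is greater than the Performance Goal (PG) of 80.7" percent (Appendix I 4.3). Appendix I 9.4.1 says: "The exact test against PG will be performed for the primary endpoint in the analysis population".

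The set for that test is described in two ways:

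- Main protocol 3.2 takes the first 220 European XTR patients "with evaluable APS data will be included in the XTR PMCF Study as described in Appendix 1".
- Appendix I takes consecutive consented patients, at least 220 (1.1). They enter on XTR treatment (3.1) or on XTR implant (5.4, 6.2.1). None of these sections requires an evaluable APS.

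On missing outcomes, Appendix I 9.4.4 lets the 30-day echo stand in for an unavailable or unassessable discharge echo, and then says: "All analyses will be based on available data with missing data excluded". Death or mitral valve surgery before discharge counts as failure without an echo (Appendix I 4.1, 9.1). Main protocol 3.2 requires echoes to be submitted at baseline, discharge, 30 days and 12 months. Appendix I 6.3 places post-treatment echoes under the same rule as other tests: "Clinical Assessments and Laboratory / Clinical Tests should be conducted per standard of care".

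**The concern.** Entry to a confirmatory test should not depend on whether its outcome was observed. Under main protocol 3.2 an XTR patient without a gradable echo is passed over and the next evaluable patient fills the place. The analysed number is still 220, and nothing in it shows how many were skipped. Under Appendix I the same patient is in the set but leaves the denominator through 9.4.4. The first route hides the loss and the second does not, but both give an evaluable-only success rate.

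The safeguards leave a gap. One example is a patient without a usable discharge echo who goes home and dies before the 30-day echo. That patient has no APS value and did not die before discharge, so is not a failure by rule and is excluded.

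If such patients succeed less often than the rest, the evaluable-only rate overstates the rate in all treated patients, and the 80.7% goal can be passed too easily. This test serves the CE-mark follow-up requirement (Protocol 1.0).

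**Working it through.** **Inputs from the documents.** n = 220 (Appendix I 9.3); goal p0 = 0.807 (4.3); "One-sided type I error rate = 0.05" (9.3); exact test (9.4.1). The assumed true APS rate and the power are redacted, so 220 cannot be reproduced, only bracketed.

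**Inputs assumed.** The missing fraction d and the APS rate q among missing patients. The documents give neither, so a range is shown.

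**1. Pass mark.** Find the smallest x with P(X ≥ x | 220, 0.807) ≤ 0.05.

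- x = 187: probability 0.060, lower bound 80.46%, fails.
- x = 188 (85.5%): probability 0.041, lower bound 80.96%, passes.

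The pass mark is 188/220 and the actual alpha is 4.1%.

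**2. Is 220 plausible?** Exact power of 80% needs a true rate of 87.1% (220 × 0.871 ≈ 192 successes). Power of 90% needs 88.1% (220 × 0.881 ≈ 194). So 220 fits an assumed rate of about 87–88%, but this cannot be confirmed.

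**3. False-pass probability.** Let the true rate in all treated patients be exactly 0.807. The rate among evaluable patients is then

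p_e = (0.807 − d·q) / (1 − d),

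and the false-pass probability is P(X ≥ 188 | 220, p_e). For example, d = 0.05 and q = 0.50 give (0.807 − 0.025)/0.95 = 0.8232, hence 12.8%.

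| APS in missing patients (q) | 2% missing | 5% missing | 10% missing |
|---|---|---|---|
| 80.7% (same as the rest) | 4.1% | 4.1% | 4.1% |
| 70% | 4.8% | 6.3% | 9.7% |
| 50% | 6.6% | 12.8% | 33% |

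**4. Tipping point, every missing patient a failure.** Keep all patients up to the 220th evaluable one, so N = 220 + m. Find the smallest m at which x falls below the exact pass mark for N.

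| Observed | m that reverses it | Share of N | Pass mark at that N |
|---|---|---|---|
| 189/220 (85.9%) | 2 | 2/222 = 0.9% | 190 |
| 192/220 (87.3%) | 6 | 6/226 = 2.7% | 193 |
| 194/220 (88.2%) | 8 | 8/228 = 3.5% | 195 |
| 198/220 (90.0%) | 13 | 13/233 = 5.6% | 199 |
| 209/220 (95.0%) | 26 | 26/246 = 10.6% | 210 |

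If half of the missing patients were successes (rounded down), 194/220 reverses only at 19 missing (19/239 = 7.9%) and 198/220 at 31 (31/251 = 12.4%).

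**5. The same under Appendix I, without refilling.** Suppose 220 are treated and 11 (5%) are unevaluable. Available-case analysis has n = 209 and passes at 179. With missing counted as failure the mark is 188 of 220. Results from 179 to 187 successes pass the first and fail the second, so the issue does not depend on replacement.

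**The case against.** **Hidden text.** Appendix I 9.2 shows no text and 9.4.1 has redacted blocks after the hypotheses. A population definition or a sensitivity analysis could sit there. This stands, and the request has to be conditional on it. It does not remove the visible rules in main protocol 3.2 and Appendix I 9.4.4.

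**Safeguards.** The clearest acute failures need no echo, submission of the discharge and 30-day echoes is required, and the 30-day window of −14/+60 days (Protocol 6.4) lets an echo from day 16 to day 90 serve as fallback. This stands: the gap is reduced, but not closed.

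**Direction unknown.** Nothing in the documents shows that missing patients do worse. If they match the rest there is no bias, and if they do better the test is conservative. A reader might infer that the 5% error rate holds only if the two groups match. That is too strong: because the exact alpha is 4.1%, it still holds at 2% missing with 70% APS (4.8%).

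**Refilling rests on one sentence.** Skipping and refilling follow from main protocol 3.2 alone, and Appendix I points the other way. A reader might state replacement as settled fact, but the documents support only a conflict.

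**The no-replacement rule.** A reader might also see a contradiction with Protocol 5.10, "Subjects will not be replaced". That sentence closes a paragraph on discontinued subjects. A patient with unevaluable APS has not discontinued and stays in the main study, so 5.10 does not bear on this point.

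**Conclusion.** The concern holds in a limited form. The documents define the set for the only powered test in two incompatible ways. Under both, patients with no usable echo and no pre-discharge death or mitral surgery are excluded, and no visible analysis tests how much that matters.

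The size is conditional on assumed missing rates and outcomes. At up to 5% missing, the false-pass probability runs from 4.1% (no difference) to 12.8% (50% APS among the missing). Reversal by a few percent missing is a risk only near the pass mark: if all missing patients are failures, 2.7–3.5% is enough at 192–194 successes. That is the result to expect if the study was planned at 80–90% power. At 95% observed success it takes 10.6%. It would be wrong to conclude that the test is biased, or that a pass could not be trusted. The documents show only that its robustness cannot be judged from what is planned and visible.

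**What to change.** 1. Reconcile main protocol 3.2 with Appendix I 1.1, 3.1, 5.4 and 6.2.1. Define the set by consecutive procedure date, whether or not APS is evaluable. If 220 evaluable patients are wanted for power, continue to the 220th and keep everyone treated up to then in the set.
2. Report the number of patients with unevaluable APS, and the reasons.
3. Unless the redacted text already does so, pre-specify in Appendix I 9.4.1 and 9.4.4 a sensitivity analysis: the same exact test with unevaluable APS counted as failure, together with the number of missing failures that would reverse the result. Describe a pass as robust to missing echoes only if it survives this.

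The cost is a wording change and one extra table, with no new patients or assessments. The downside is a slightly less favourable margin over the goal in the sensitivity analysis.

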3.3 Measures Taken to Avoid and Minimize Bias

3.3.1 Study Flow

Study sites are instructed to consent consecutive subjects prior to MitraClip procedure. All patients eligible to receive a MitraClip (i.e. no evidence of thrombus) will included in the study analysis.

3.3.2 Clinical Events Committee

The safety endpoint for the study will include oversight by an independent CEC which will issue the final decision on reported MAEs.

3.3.3 Steering Committee

An independent steering committee will have oversight on the study.

3.4 Early Termination of the Clinical Study

No formal statistical rule for early termination of this study is defined.

The Sponsor reserves the right to discontinue the study at any stage or reduce the follow up period with suitable written notice to the investigator. Possible reason(s) may include, but are not limited to:

- Unanticipated adverse device effect (UADE) occurs and it presents an unreasonable risk to the participating subjects.
- The Steering Committee makes a recommendation to stop or terminate the study

Should the study be discontinued by the Sponsor, patients will be followed up as per routine hospital practice with device related Adverse Events (AEs) being reported to the Sponsor as per vigilance/commercial reporting requirements.

In the event of study termination, the investigator shall return all clinical study materials to the Sponsor, and provide a written statement as to why the premature termination has taken place to the IRB/EC (if applicable). All applicable Clinical Investigation documents shall be subject to the same retention policy as detailed in section 12 of the Protocol entitled, 'Data Handling and Record Keeping'.

4.0 STUDY ENDPOINTS

4.1 Safety and Performance Measures

- Safety
The assessment of safety will include all occurrences through 30 days post procedure.
Occurrence of Major Adverse Events (MAE) at 30 days
MAE is defined as a composite of all-cause Death, Myocardial Infarction, Stroke, or non-elective Cardiovascular (CV) surgery for device related complications (CEC adjudicated).
- Performance
The assessment of performance measures will include all data reported at 30-day visits for this study.
MR Reduction to $\leq 2+$ at 30 days

4.2 Acute Measures

- Acute Procedural Success (APS) defined as successful implantation of the MitraClip® device with resulting MR severity of 2+ or less on discharge Echocardiogram (30-day

echocardiogram will be used if discharge is unavailable or uninterpretable). Subjects who die or undergo mitral valve surgery before discharge are considered to be an APS failure

- Acute Device Success defined as successful implant of the MitraClip device without the occurrence of a Device-Related Complication (including mitral valve stenosis, device embolization, Single Leaflet Device Attachment (SLDA), Iatrogenic atrial septal defect, or myocardial perforation) through discharge.
- Use of MitraClip NTR or MitraClip XTR: to include the percentage of cases with each device and an assessment of reason for device selection
- Procedure Time: defined as the time elapsed from the first intravascular catheter placement or trans-esophageal echocardiogram (TEE) to the removal of the last catheter and TEE
- Number of Clips Implanted
- Number of Attempted Grasps defined as the number of attempts to stabilize leaflets by the open Clip
- User feedback
- Device-Related Complications defined as the occurrence of one the following adverse events that is determined by investigator assessment to be probably, possibly or definitely related to the MitraClip device.
 - Mitral valve stenosis
 - SLDA
 - Device Embolization
 - Iatrogenic atrial septal defect
 - Myocardial perforation
 - Need for mitral valve replacement instead of repair due at least in part to the MitraClip procedure or the presence of the MitraClip device
- In-hospital MAE defined as the number of MAEs that occur prior to discharge from hospitalization in which MitraClip Procedure was performed
- MR Reduction to $\leq 1+$ at 30 days

4.3 Clinical Measures

(Discharge, 1, 6 and 12 months):

- All-cause Mortality
- Heart Failure Hospitalization
- MAE as defined above
- Device-Related Complications as defined above

4.4 Functional Improvement Measures

(Baseline, Discharge & 12 months)

- New York Heart Association (NYHA) functional class improvement
- Quality of Life (QOL) assessed using the Kansas City Cardiomyopathy Questionnaire (KCCQ)

4.5 Site Reported Echocardiographic Measures

(Baseline, Post Procedure, 1, & 12 months):

- MR Severity Grade
- Effective Regurgitant Orifice Area (EROA) as measured by measured by PISA method
- Coaptation Measures (depth/length)

- *Coaptation depth: Coaptation depth is defined as the distance from the plane of the mitral valve annulus to the first point of leaflet coaptation in the atrial-to-ventricular direction in the four-chamber view.*
- *Coaptation length: Coaptation length is defined as the vertical length of leaflets that is in contact, or is available for contact, during systole in the atrial-to-ventricular direction in the four-chamber view.*
- Flail Measures (gap/width)
 - *Flail Gap: Measured as the greatest distance between the ventricular side of the flail segment to the atrial side of the opposing leaflet. This distance is measured perpendicular to the plane of the annulus in two views and the largest measurement is used. The two views for measurement are the four-chamber long axis (LAX) view and the left ventricular outflow tract (LVOT) view.*
 - *Flail Width: Measured as the width of the leaflet segment that moves in and out of plane during systole in the short axis (SAX) view.*
- Grasping Area Anatomy (measure cleft or scallop if significant)
- Assess chordal support
- Regurgitant Jet(s) Position and Quantity
- TR Severity: None, Mild, Moderate or Severe

4.6 Core Lab Subgroup:

Subjects with evaluable echocardiograms may be selected for a more detailed assessment by an independent core lab. Pre-defined criteria will be used to identify eligible subjects for this assessment. A minimum of 100 subjects will be randomly selected from this eligible population.

5.0 SUBJECT SELECTION AND WITHDRAWAL

5.1 Subject Population

This MitraClip® EXPAND Study will enroll male and female subjects with symptomatic mitral regurgitation who satisfy the inclusion and exclusion criteria and who are treated with the next generation MitraClip NTR System and/or MitraClip XTR System. The study will conduct analysis on approximately 1,000 subjects. Subjects must provide written informed consent prior to their data being submitted to the Study.

5.1.1 Anatomy Complexity

For analysis, subjects will be sorted into two groups based on valve anatomies identified to be important for MitraClip placement ^{26, 27, 28}

²⁶ Boerlage-van Dijk K, et al, Mitral valve anatomy predicts outcome of MitraClip implantation, *Int J Cardiol* (2014)

²⁷ Ambrožič J, Cvijič M, Bervar M, Bunc M., *Wien Klin Wochenschr*. Initial Slovenian experience with MitraClip therapy : Careful selection of patients is crucial for optimal outcome. 2017 Dec 4. doi: 10.1007/s00508-017-1295-7. [Epub ahead of print]

²⁸ Lesevic H, Karl M, Braun D, Barthel P, Orban M, Pache J, Hadamitzky M, Mehilli J, Stecher L, Massberg S, Ott I, Schunkert H, Kastrati A, Sonne C, Hausleiter J. Long-Term Outcomes after MitraClip Implantation According to the Presence or Absence of EVEREST Inclusion Criteria. *Am J Cardiol*. 2017; 119:1255-1261.

Group 1 (Complex Subjects):

If one or more of the following characteristics are present:

- Primary Jet outside of A2P2
- Presence of more than one significant jet
- Wide Jet
- Small Valve
- Calcified landing zone
- Minimal leaflet tissue for attachment (due to small coaptation length or too much coaptation depth)
- Presence of severely degenerative leaflets or wide flail gaps or widths

Group 2 (Non-Complex Subjects):

All subjects who do not qualify as a complex subject will be classified as Non-Complex subjects whose characteristics are similar to subjects enrolled in the EVEREST II trial.

5.2 Subject Screening and Informed Consent

5.2.1 Subject Screening

The hospital will follow their standard of care procedures for determining if a patient is eligible for treatment with a MitraClip® System. Consecutive MitraClip patients should be asked to provide consent for participation in the study if they are eligible per the inclusion/exclusion criteria (see section 5.2.3). Upon echocardiographic verification that there is no evidence of intracardiac, inferior vena cava (IVC) or femoral venous thrombus per IFU requirements; the MitraClip procedure should be attempted. The procedure is considered attempted when the MitraClip delivery system is introduced. All consented patients with an attempted MitraClip procedure will be included in the study analysis.

5.2.2 Informed Consent

Patient Informed Consent Form must receive approval of Sponsor and EC/IRB prior to beginning enrollment into the MitraClip® EXPAND Study.

The Investigator or designee, who has been trained on the Protocol, will explain the nature and scope of the study, potential risks and benefits of participation, and answer questions for the subjects. For this study the subject will be treated per standard of care and must consent only to data collection (including echocardiogram) and follow-up visit schedule. All subjects (or legally authorized subjects' representatives if applicable) must sign, date and time (if required) the Institutional Review Board (IRB)/Ethics Committee (EC) approved informed consent prior to any clinical study-specific procedures. Obtaining the consent and provisioning of a copy to the subject, along with the date and time must be documented in the subject's medical records. In addition, the signed informed consent must be kept in the subject's medical records.

At sites in the United States, an authorization for use and disclosure of the subject's protected health information, in accordance with the Health Insurance Portability and Accountability Act (HIPAA), must be obtained from the subject or their legally authorized representative. Per site requirements/preference HIPAA elements may be incorporated into the Informed Consent Form (ICF) or it may exist as a standalone document.

If approved by IRB/ EC, subjects from vulnerable populations may be enrolled in the study. ISO14155 definition of vulnerable population: Defined as subject whose willingness to volunteer in a clinical investigation could be unduly influenced by the expectation, whether justified or not, of benefits associated with participation or of retaliatory response from senior members of a hierarchy in case of refusal to participate. Examples of populations which may contain vulnerable subjects include: Individuals with lack of or loss of autonomy due to immaturity or through mental disability, persons in nursing homes, children, impoverished persons, subjects in emergency situations, ethnic minority groups, homeless persons, nomads, refugees, and those incapable of giving informed consent. Other vulnerable subjects include, for example, members of a group with a hierarchical structure such as university students, subordinate hospital and laboratory personnel, employees of the sponsor, members of the armed forces, and persons kept in detention.

